4. LIST OF ABBREVIATIONS

The following abbreviations are used in this study protocol.

Abbreviation or specialist term	Explanation
ADT	antidepressant therapy
AE	adverse event
ATRQ	Massachusetts General Hospital Antidepressant Treatment Response Questionnaire
BMI	body mass index
BUP	buprenorphine
CGI-S	Clinical Global Impression–Severity
COWS	Clinical Opiate Withdrawal Scale
CRO	contract research organization
C-SSRS	Columbia Suicide Severity Rating Scale
CSA	Clinical Study Agreement
CST	Clinical Surveillance Team
CYP	cytochrome P450
DSM-IV-TR	Diagnostic and Statistical Manual of Mental Disorders, 4 th Edition, Text Revision
ECG	electrocardiogram
eCRF	electronic case report form
FAS	full analysis set
GCP	Good Clinical Practice
HAM-A	Hamilton Rating Scale for Anxiety
HAM-D	17-item Hamilton Rating Scale for Depression
HbA1c	glycosylated hemoglobin
HIV	human immunodeficiency virus
IB	Investigator’s Brochure
ICF	informed consent form
ICH	International Conference on Harmonisation
IEC	independent ethics committee
IRB	institutional review board
IRT	interactive response technology

Abbreviation or specialist term	Explanation
IUD	intrauterine device
MADRS	Montgomery-Åsberg Depression Rating Scale
MDD	major depressive disorder
MDE	major depressive episode
MedDRA	Medical Dictionary for Regulatory Activities
MINI	Mini International Neuropsychiatric Interview
OTC	over-the-counter
PCS	potentially clinically significant
PK	pharmacokinetic(s)
PLI	prospective lead-in
QTcB	corrected QT interval – Bazett’s formula
QTcF	corrected QT interval – Fridericia’s formula
SAE	serious adverse event
SAP	statistical analysis plan
SL	sublingual
SIGH-A	Structured Interview Guide for the Hamilton Rating Scale for Anxiety
SIGH-D	Structured Interview Guide for the Hamilton Rating Scale for Depression
SIGMA	Structured Interview Guide for the Montgomery-Åsberg Depression Rating Scale
SNRI	serotonin-norepinephrine reuptake inhibitor
SSRI	selective serotonin reuptake inhibitor
TEAE	treatment-emergent adverse event
WHO-ATC	World Health Organization Anatomical Therapeutic Chemical

5. INTRODUCTION

Alkermes is developing ALKS 5461, a fixed-dose combination tablet consisting of buprenorphine (BUP) and samidorphan in a 1:1 (weight/weight) ratio for once-daily sublingual administration for use as an adjunctive therapy to antidepressants for the treatment of major depressive disorder (MDD).

MDD is a serious, and in some cases life-threatening, condition. Current therapy is limited and insufficient. Selective serotonin reuptake inhibitors (SSRI) or serotonin-norepinephrine reuptake inhibitors (SNRI) are recommended as first-line therapy; however, the large majority of patients do not experience an adequate response [Rush, 2006]. For patients with MDD who have an inadequate response to approved first-line antidepressant therapy (ADT) the only currently approved agents for adjunctive treatment are atypical antipsychotics. However, this class of medicines is associated with serious toxicity, including tardive dyskinesia, which may be irreversible, as well as neuroleptic malignant syndrome and agranulocytosis, both of which are potentially fatal. These conditions and other side effects of the atypical antipsychotics commonly lead to discontinuation of treatment [Spielmans, 2013].

The development of an adjunctive treatment that avoids the toxicity associated with atypical antipsychotics is an important step toward addressing the suboptimal treatment of MDD and the related public health consequences. ALKS 5461 offers a unique mechanism of action for the treatment of MDD, modulation of the opioid system. From 1982 to the present, there have been at least 8 published studies of BUP in depressed patients [Spielmans, 2013]. These studies demonstrated striking antidepressant effects with BUP treatment, particularly in patients with MDD who have had multiple prior inadequate responses to therapy. Despite this evidence of efficacy with BUP, the risk of diversion, abuse, and dependence have precluded routine clinical use of BUP, and opioids in general, in the treatment of depression.

ALKS 5461 is a fixed-dose combination of BUP (a μ -opioid receptor partial agonist) and samidorphan (a μ -opioid receptor antagonist). Samidorphan is a new chemical entity optimized for high potency and high sublingual (SL) bioavailability to facilitate co-formulation with BUP for SL administration. ALKS 5461 was specifically designed to confer therapeutic benefits in the treatment of MDD through modulation of the opioid system. The inclusion of samidorphan in the ALKS 5461 combination is intended to counteract the subjective, rewarding and addictive properties of BUP and thus address the risk of abuse and dependence.

Subjects treated with ALKS 5461 in Phase 1 and the Phase 2 studies showed substantial and clinically important improvements in depressive symptoms compared with those treated with placebo. Safety and tolerability data from these studies showed that ALKS 5461 was safe and generally well tolerated, and further no evidence has been found that ALKS 5461 is associated with motor disorders or metabolic dysregulation, the important toxicities associated with atypical antipsychotics. All together these findings indicate that ALKS 5461 has the potential to address an unmet medical need in this serious and in some cases life-threatening, condition.

Full summaries of nonclinical and clinical results available to date on the pharmacokinetics (PK), safety, and efficacy of ALKS 5461, as well as of samidorphan and buprenorphine as individual and co-administered therapeutic agents are summarized in the [Investigator's Brochure](#) (IB).

5.1. Study Rationale

Subjects with MDD and an inadequate response to concomitant ADT who were treated with ALKS 5461 in both a Phase 1 study (ALK33BUP-201) and a Phase 2 study (ALK5461-202) showed substantial and clinically important improvements in depressive symptoms compared with those who received placebo. Safety and tolerability data from these studies showed that ALKS 5461 was safe and generally well tolerated, and further showed no evidence that ALKS 5461 is associated with motor disorders or metabolic dysregulation, the important toxicities associated with atypical antipsychotics.

In the clinical trials of ALKS 5461 to date, however, only data on the short-term safety and tolerability of ALKS 5461 have been collected. This study is designed to assess long-term safety and tolerability of ALKS 5461, as well as to explore treatment effect over time.

5.2. Dose Selection

Note: Throughout this protocol ALKS 5461 dose levels will be referred to as dose of BUP/samidorphan expressed as weight in mg (eg, a 2 mg BUP:2 mg samidorphan dose will be expressed as ALKS 5461 2/2).

Doses for the current study were identified based on completed studies of ALKS 5461 including a drug-drug interaction study of BUP with samidorphan (ALK33-008), and a Phase 2 (ALK5461-202) study in adults with MDD and inadequate response to concomitant ADT.

[Study ALK33-008](#), the drug-drug interaction study, showed that a 1:1 ratio of BUP and samidorphan in doses up to 8/8 provided maximal blockade of objective and subjective μ opioid agonist effects of BUP. Thus doses in the current study, which use a 1:1 ratio, are expected to mitigate BUP's subjective, rewarding, and addictive effects.

[Study ALK5461-202](#) was a Phase 2, multicenter, randomized, double-blind, placebo-controlled, sequential-parallel-comparison-design clinical trial which evaluated ALKS 5461 at doses of 2/2 and 8/8. The ALKS 5461 2/2 dose was shown to be safe, well tolerated, and efficacious. After 4 weeks of dosing, statistically significant improvements from baseline were found for the ALKS 5461 2/2 group versus the placebo group for the primary efficacy endpoint (change in the 17-item Hamilton Rating Scale for Depression [HAM-D] total score), as well as several secondary endpoints, (change in Montgomery-Åsberg Depression Rating Scale [MADRS] total score and Clinical Global Impression - Severity [CGI-S] score). Additionally, the rate of treatment response and the rate of remission as defined by MADRS scores were significantly higher in the ALKS 5461 2/2 group versus the placebo group.

The selection of the ALKS 5461 2/2 dose is further supported by its improved tolerability profile compared with results for the ALKS 5461 8/8 dose.

6. OBJECTIVE

The objective of this study is to assess the long-term safety and tolerability of ALKS 5461 for use as an adjunctive therapy to antidepressants for the treatment of MDD.

7. SELECTION AND WITHDRAWAL OF SUBJECTS

7.1. Subject Inclusion Criteria

7.1.1. All Subjects

In order to qualify for participation in this study, all subjects must meet all of the following criteria:

1. Be willing and able to provide informed consent
2. Be willing and able to follow the study procedures as outlined in the protocol, including adherence with both approved antidepressant therapy (ADT) and study drug regimen
3. Agree to use an approved method of contraception for the duration of the study unless surgically sterile or postmenopausal (See [Section 8.4.1](#) for details)
4. Have the potential to safely benefit from the administration of ALKS 5461, in the opinion of the investigator

7.1.2. New Subjects

In order to qualify for participation in this study, in addition to meeting the criteria for all subjects presented in Section 7.1.1, New Subjects must also meet all of the following criteria:

5. Be between 18 and 70 years of age, inclusive
6. Have a body mass index (BMI) 18.0 - 40.0 kg/m²
7. Have not been randomized in a prior study of ALKS 5461 within 2 years
8. Have a Diagnostic and Statistical Manual of Mental Disorders, Fourth Edition, Text Revision (DSM-IV-TR) MDD diagnosis at screening, as assessed and confirmed by the Mini International Neuropsychiatric Interview (MINI) administered by qualified site staff. The diagnosis of MDD must be considered by the investigator as the primary source of current distress and functional impairment
9. Have a current major depressive episode (MDE) lasting 8 weeks to 24 months
10. Have been treated with an adequate dose of an approved ADT during the current MDE for at least 8 weeks, with the same, adequate dose over the last 4 weeks, which is expected to remain stable throughout the study
11. Have an inadequate response to current ADT and up to 1 prior ADT during the current MDE. An inadequate response is defined as less than a 50% reduction in depressive symptom severity during a course of treatment at least 8 weeks in duration with an adequate dose of an approved ADT, as assessed on-site using the Massachusetts General Hospital Antidepressant Treatment Questionnaire (ATRQ)

(NOTE: If a subject had an adequate response to an ADT in the past, but now has relapsed on the same ADT at the same or lower dose and is experiencing a new MDE, this would not represent an adequate trial of an ADT for this new MDE)

12. Have a HAM-D total score of ≥ 14 at Visit 1 and ≥ 10 at Visit 2

7.1.3. Continuing Subjects

In order to qualify for participation in this study, in addition to meeting the criteria for all subjects presented in [Section 7.1.1](#), Continuing Subjects must also meet the following criterion:

13. Have completed the treatment period of ALK5461-205, ALK5461-206, ALK5461-207, or ALK5461-210 within 10 days of Visit 2

7.1.4. Lead-in Subjects

In order to qualify for participation in this study, in addition to meeting the criteria for all subjects presented in [Section 7.1.1](#), Lead-in Subjects must also meet all of the following criteria:

14. Have completed the prospective lead-in (PLI) of study ALK5461-205, ALK5461-206, or ALK5461-207 within the past 10 days; criteria for completion of the PLI includes 1) at least 8 weeks of ADT with at least 5 weeks at the minimally effective dose and 2) completion of Visits 1a through 1f

15. Have demonstrated a treatment response during the PLI of the antecedent study, but failed to achieve remission from MDD, as determined in an interactive voice or web response system (IxRS) using masked criteria

7.2. Subject Exclusion Criteria

7.2.1. All Subjects

No individuals may participate in this trial if they meet any of the following criteria:

1. Have any finding that in the view of the investigator or medical monitor would compromise the safety of the subject or affect their ability to fulfill the protocol visit schedule or visit requirements
2. Have a positive test for drugs of abuse at screening or Visit 2 (exception: a positive screen for benzodiazepine may not be exclusionary when such medication is medically indicated for insomnia)
3. Are pregnant, planning to become pregnant, or breastfeeding during the study

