For Continuing Subjects, Visit 2 of this study must occur within 10 days of the subject's end of treatment visit in the prior study. Completed assessments taken at the end of treatment visit of the antecedent study do not need to be repeated at Visit 2 of this study. At Visit 2, all eligible, consenting subjects will begin the treatment period. Subjects entering the study already receiving ALKS 5461 will not require titration; all other subjects will require a 1-week ALKS 5461 titration period. Depending on the antecedent study, the titration may be blinded. Regardless of method of entry, all subjects will have been taking an SSRI, SNRI, or bupropion for at least 8 weeks at the beginning of the treatment period (Visit 2), and at an adequate dose for at least

5 weeks. Table 1 below shows the Week 1 titration and blinding schemes for the subjects entering by each path.

Table 1: Week 1 Titration and Blinding by Entry Dose and Antecedent Study

Dose Upon Study Entry	Antecedent Study	Week 1 Blinding	Week 1 Dosing Scheme
No study drug being given	
 New Subjects Lead-in Subjects ALK5461-205 (after 1-week discontinuation period) 	Unblinded	1-Week Titration 
 Days 1–3: ALKS 5461 0.5/0.5 Days 4–7: ALKS 5461 1/1
Placebo	
 ALK5461-206 ALK5461-207 	Blinded	
 Days 8–364: ALKS 5461 2/2
ALKS 5461 1/1	
 ALK5461-207 	Blinded	No Titration 
 Days 1–364: ALKS 5461 2/2
ALKS 5461 2/2	
 ALK5461-206 ALK5461-207 	Blinded	
	
 ALK5461-210 	Unblinded	

Dosing is described in detail in [Section 9.1.2](#). From Week 2 to 52, all participating subjects will take ALKS 5461 2/2 and an approved ADT, with allowable dose adjustments for tolerability as described in [Section 9.5](#).

Study staff will administer the first dose of ALKS 5461 at Visit 2 (Day 1). From that point on during the treatment period, according to the schedule of visits as shown in [Table 2](#), the staff will dispense ALKS 5461 for subjects’ self-administration. Subjects will be advised to take the study drug at bedtime.

During the 52-week treatment period, subjects will return to the clinic for periodic scheduled visits (Visits 2-14) at which safety, tolerability, and treatment effect over time will be assessed.

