- ⁱ Centralized drug screen testing at screening, local drug screen testing (via dipstick) for all other time points. The urine drug screen at Visit 1 may be repeated based on investigator judgment. The test can also be repeated at any time during the study, should the investigator feel it is warranted
- ^j Serum pregnancy testing at screening; urine pregnancy testing at all other visits
- ^k At screening the "Baseline" version of the C-SSRS will be administered and at all other visits the "Since Last Visit" version will be administered
- ^l COWS to be administered by a medical professional
- ^m All medications (prescription and non-prescription, including vitamins and herbal supplements) including ADT taken within 30 days will be recorded at screening. Any changes will be recorded at subsequent visits
- ⁿ Subject will be queried at screening on illicit substances used within 30 days, with updates made at each subsequent visit
Note: additional dispensation visits may be required based on country specific regulatory requirements. No other activities or assessments are done on these days.
- ^o The MADRS should be administered prior to the HAM-D, CGI-S and HAM-A on visits when multiple assessments are scheduled
- ^p First dose of ALKS 5461 (at Visit 2) to be administered on-site; ALKS 5461 to be dispensed at each indicated visit for subjects to self-administer starting on Day 2. Self-administration should be recommended to occur at bedtime
- ^q Via pill count and subject query
- ^r Via subject query
- ^s One PK blood sample will be collected during each indicated visit from consenting subjects enrolled in the United States only. When PK and safety blood samples are scheduled to be collected on the same day, efforts should be made to collect both samples during the same draw.
- ^t Dispense card on Visit 2; confirm possession of card at each subsequent visit and re-dispense if necessary

Table 3: Schedule of Assessments, Safety Follow-up Period

Evaluation	Safety Follow-up Period										
	1 (+1)	2 (+1)	3 (+1)	4 (+1)	5 (+1)	6 (+1)	7 (+1)	10 (+2)	14 (±2)	21 (+2)	28 (±2)
Days post end of treatment:	366	367	368	369	370	371	372	375 (+2)	379 (±2)	386 (+2)	393 (±2)
Study Day:	366	367	368	369	370	371	372	375 (+2)	379 (±2)	386 (+2)	393 (±2)
Visit ^a	15	Phone	Phone	Phone	Phone	Phone	16	Phone	17	Phone	18
Adverse Event Monitoring ^b	X	X	X	X	X	X	X	X	X	X	X
Concomitant Med Review ^c	X	X	X	X	X	X	X	X	X	X	X
Illicit Substances Review ^c	X						X		X		X

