8.3.15.3. Urine Drug Screening

New Subjects will undergo urine drug screening for drugs of abuse at Visit 1 and laboratory analysis will be centralized. At all other time points specified in [Table 2](#) and [Table 3](#), all participating study subjects will have urine drug screening via dipstick; results will be analyzed by the local laboratory.

Drug screening will be performed for amphetamines, barbiturates, benzodiazepines, cocaine (metabolite), tetrahydrocannabinol, opioids, and phencyclidine. The opioid panel to be performed at screening for New Subjects (analyzed centrally) will include BUP, codeine, hydrocodone, hydromorphone, methadone, morphine, oxycodone, and oxymorphone. Drug screens administered at all other visits as specified in [Table 2](#) and [Table 3](#) (analyzed locally) will include all aforementioned opioids.

Negative urine drug screening at Visit 1 and Visit 2 will be required for a subject to enter in the study. However, an exception may be made for a benzodiazepine, when such medication is medically indicated for insomnia.

The urine drug test at screening may be repeated based on investigator judgment. The test can also be repeated at any time during the study, should the investigator feel it is warranted. Action taken in response to a positive urine drug screen after Visit 2 should be based on a medical evaluation in consultation with the medical monitor.

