8.4.2.2. Prohibited Medications

The use of any kind of adjunctive therapy, other than ALKS 5461, at an adequate dose and duration in combination with an ADT at any time during the current MDE for the purpose of augmenting the effects of the ADT is prohibited. Adjunctive therapy other than ALKS 5461 is prohibited from screening through the final follow-up visit. Prohibited adjunctive therapies include, but are not restricted to the following:

- atypical antipsychotics (eg, aripiprazole, quetiapine, olanzapine)
- monoamine oxidase inhibitors (eg, phenelzine, tranylcypromine, selegiline)
- lithium
- tricyclic antidepressants (eg, amitriptyline, nortriptyline, desipramine)
- psychostimulants (eg, methylphenidate, dextroamphetamine/ amphetamine)
- bupropion
- BUP

The use of opioid agonists (eg, codeine, oxycodone, tramadol, morphine) or opioid antagonists (eg, naloxone, naltrexone) within 14 days before screening through the final follow-up visit is prohibited. Use of extended-release opioid antagonists within 2 months prior to screening through the final follow-up visit is prohibited.

The initiation or dose adjustment of hormone replacement therapy (including testosterone) or an oral contraceptive within 30 days of screening is prohibited. Such therapy is permissible if a stable dose of hormone replacement therapy or oral contraceptive is taken for at least 30 days prior to screening and the same stable dose is expected to be taken throughout the study.

Hypnotic agents for insomnia (eg, benzodiazepines, zolpidem, trazodone) are not permitted if started within 30 days of screening or if started at any time during the study. Such agents are permitted if they have been used stably for at least 30 days before screening not more than 3 times/week, and are expected to be used stably at ≤ 3 times/week throughout the study. For an insomnia indication, benzodiazepine is permissible if equivalent to ≤ 2 mg/day of lorazepam, trazodone up to 100 mg/day, zolpidem or zaleplon up to 10 mg/day, or Ambien CR up to 12.5 mg/day. Hypnotic agents are not permitted within 30 days prior to screening through the final follow-up visit if prescribed for an indication other than insomnia.

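### The entry drug screen tests for buprenorphine and exempts only benzodiazepines, yet the protocol enrols Continuing Subjects already taking buprenorphine-containing ALKS 5461

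*Protocol*

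**What the plan says.** Four parts of the protocol bear on this.

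- **Eligibility.** Exclusion 2 (Section 7.2.1, All Subjects) reads "Have a positive test for drugs of abuse at screening or Visit 2 (exception: a positive screen for benzodiazepine may not be exclusionary", and then confines the exception to insomnia. Section 8.3.15.3 says "Negative urine drug screening at Visit 1 and Visit 2 will be required for a subject to enter in the study" and gives the same single exception. It leaves the response to a positive screen to medical judgment only after Visit 2 has passed.
- **Panel.** Section 8.3.15.3 says "The opioid panel to be performed at screening for New Subjects (analyzed centrally) will include BUP, codeine" and other named opioids. The screens at all other visits (those "analyzed locally) will include all aforementioned opioids") cover the same list. Table 2, footnote i, specifies "local drug screen testing (via dipstick) for all other time points".
- **Entry scheme.** Section 5 states that "ALKS 5461 is a fixed-dose combination of BUP" and samidorphan. Section 8.1 says "Subjects entering the study already receiving ALKS 5461 will not require titration". Table 1 lists entrants on 1/1 from -207 and on 2/2 from -206, -207 and -210.
- **Carry-forward.** Criterion 13 (Section 7.1.3) allows at most 10 days between completing antecedent treatment and Visit 2. Within that window, Section 8.1, Section 8.3.2 and Table 2 footnote c let antecedent assessments replace Visit 2 ones.

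For comparison, Section 8.4.2.2, which lists BUP among the banned adjuncts, says "Adjunctive therapy other than ALKS 5461 is prohibited from screening through the final follow-up visit".

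**The concern.** The rollover of subjects already on active drug is a deliberate part of the design. SAP Section 3.1 builds one of its two summary groups, prior exposure to ALKS 5461, from Continuing Subjects who had active treatment. The entry screen, as worded, looks for a component of the drug those subjects are taking and contains no exemption for it.

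A site that applies exclusion 2 to the letter would turn such subjects away. A site that looks past it would enrol subjects who fail a criterion as written, and someone must then decide whether that is a deviation under SAP Section 3.2.3. Both effects fall on the prior-exposure group alone. If sites differ, selection into that group would depend on how each site reads the text.

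There is also a conditional blinding question. Section 9.4 keeps subjects, investigators, site staff and the sponsor blind to antecedent assignment. A BUP result seen at the site could separate former active from former placebo entrants.

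**Working it through.** The plan gives no figure to reproduce, so the check sets the provisions side by side.

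**1. Is BUP on the Visit 2 panel?** Yes. Section 8.3.15.3 names BUP on the central panel and gives the local panel the same opioids. Footnote i makes every screen after screening local.

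**2. Who is on BUP at Visit 2?** Counting Table 1 by dose and source:

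| Status at entry | Source | Routes | Week 1 |
|---|---|---|---|
| No study drug | New, Lead-in, -205 | 3 | unblinded |
| Placebo | -206, -207 | 2 | blinded |
| ALKS 5461 1/1 | -207 | 1 | blinded |
| ALKS 5461 2/2 | -206, -207 | 2 | blinded |
| ALKS 5461 2/2 | -210 | 1 | unblinded |

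Total: 3 + 2 + 1 + 2 + 1 = 9 routes. On ALKS 5461: 1 + 2 + 1 = 4 of 9. Continuing routes: 9 − 2 (New, Lead-in) = 7, so 4 of 7. Of those 4, 1 + 2 = 3 are blinded and 1 is not. Blinded -206/-207 routes in all: 3 active + 2 placebo = 5. These are routes, not subjects.

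**3. Is there an exemption?** None is written for BUP from study drug. The benzodiazepine exception does not reach it, and medical judgment applies only to positives after Visit 2. Section 8.4.2.2 shows how such an exemption could be worded, but that wording is absent from Sections 7.2.1 and 8.3.15.3.

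**4. Does carry-forward settle it?** It leaves two questions open.

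- *What carries forward.* For Continuing Subjects, Section 8.1 speaks of completed assessments, without further condition. Footnote c and Section 8.3.2 speak of identical ones.
- *How a carried-forward result counts.* Exclusion 2 refers to a test at screening or Visit 2. Continuing Subjects have no screening visit, and a carried-forward screen means no test is done at Visit 2. No provision says whether the antecedent result is deemed the Visit 2 result.

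The possible cases are:

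| Antecedent screen | Wording applied | Consequence |
|---|---|---|
| Included BUP | either | No new dipstick; whether a BUP-positive result excludes is not stated |
| Omitted BUP | Section 8.1 | No new dipstick; no conflict |
| Omitted BUP | Footnote c, Section 8.3.2 | New dipstick with BUP; a positive result excludes |

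The antecedent panels are not described, so the documents do not show which row applies.

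**5. Blinding.** Exposure of the antecedent arm requires a new BUP dipstick, read at the site, in a -206 or -207 entrant. That can arise in the third row, not in the first two.

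**The case against.** The strongest reply is that the intent is plain. The exclusions on prior adjunctive BUP and on opioid use (8 and 10) apply to New Subjects only. Section 8.4.2.2 spares ALKS 5461, and Table 1 and SAP Section 3.1 expressly provide for these entrants. Later local panels also test for BUP while every subject is taking it, so the protocol cannot mean to treat study-drug BUP as abuse. All of this stands as evidence of intent. It does not repair the rule. The authors thought a legitimately used benzodiazepine needed an express exception, so a legitimate source does not excuse a positive entry screen by itself. The later panels fall under the medical-judgment clause, which the entry screen lacks.

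Second, the Section 8.3.15.3 sentence asks for negative results at both Visit 1 and Visit 2, and Continuing Subjects have no Visit 1. It cannot be applied to them word for word. That weakens it as support, but exclusion 2 refers to screening *or* Visit 2 and stands without it.

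Third, carry-forward may mean that many Continuing Subjects have no Visit 2 dipstick. This largely stands. A reader might infer that carry-forward can never help, because either the old result counts or a new test is due. The documents do not support that: under Section 8.1 an antecedent screen without BUP could suffice, and nothing says that a carried-forward result triggers exclusion 2.

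Fourth, the consequences are easily overstated. A reader might infer that the Visit 2 screen will unblind former -206 and -207 subjects. That would need a new dipstick, and Section 8.3.2 says an identical screen is not repeated within 10 days. Dosing is also open-label from Day 8. A reader might equally expect a cluster of reported deviations, but SAP Section 3.2.3 summarises only major deviations, and nothing classes a study-drug positive as major.

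**Conclusion.** The eligibility text contradicts the entry scheme and should be reconciled. For a Continuing Subject on ALKS 5461 whose Visit 2 screen is BUP-positive, the protocol gives two opposite answers. This is a stated rule that excludes intended subjects, not merely a missing detail.

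The conflict can arise on 4 of 9 entry routes (4 of 7 Continuing routes). No number of affected subjects can be derived. The documents do not say whether the dipstick turns positive at 1/1 or 2/2, how long it stays positive, how many subjects use each route, or what the antecedent panels contained. That the dipstick detects BUP at these doses is an assumption. For -205 subjects, who enter after a week off drug, any effect depends on the unstated detection window. New, Lead-in and former placebo entrants are not on study drug at Visit 2, so the conflict does not reach them.

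The documents do not show that subjects were in fact turned away, that antecedent arms will be revealed, or that major deviations will follow. The unblinding risk is conditional on a new site-read dipstick.

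**What to change.** Reconcile exclusion 2 (Section 7.2.1), Section 8.1 with Table 1, Section 8.3.15.3 and Section 9.4, and align Table 2 footnote c and Section 8.3.2 with Section 8.1 on what may be carried forward. Specifically:

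- State in Sections 7.2.1 and 8.3.15.3 how a BUP result attributable to antecedent ALKS 5461 is treated for a Continuing Subject's eligibility.
- State whether, and how, a carried-forward antecedent screen counts for exclusion 2.
- Make the handling of any BUP result the same for every -206 and -207 entrant, whatever the arm, so that no result reveals the antecedent assignment.

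The sponsor chooses the screening rule. Dropping BUP from the Visit 2 panel for all Continuing Subjects would be one way, but it has a price: non-study BUP use would go undetected at Visit 2 in former placebo and -205 entrants. The reconciliation does not require that choice.

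The cost is wording in two sections, with the cross-references brought into line, and possibly a change in how the Visit 2 BUP result is handled.
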